4.7.3.1 Safety laboratory parameters over time

For all continuous laboratory parameters listed in Section 3.4.4, absolute values and changes from baseline during the ST+LT and randomised withdrawal periods will be summarised by treatment group using descriptive statistics (including data regardless of rescue medication initiation). Visit windows are provided in Section 4.1.7.1 in order to link each laboratory test to a scheduled visit.

Unless otherwise specified, laboratory data obtained after the start of study medication dosing up to and including 4 days (30 days for liver function laboratory tests) after the last dosing date (or up to and not including the start of the LT treatment period, whichever comes first, for ST period) will be considered as obtained respectively during ST and the LT period. For the randomised withdrawal period, laboratory data collected on and after the withdrawal baseline up to and including 4 days (30 days for liver function laboratory tests) after the last dosing date in the randomised withdrawal period will be considered for the randomised withdrawal period. Laboratory data obtained from the day after the Week 56 visit up to the last visit date of the follow-up period will be considered as obtained during the follow-up period.

Shift tables (in SI units) of subjects with values in categories of low, normal, and high (based on normal ranges provided by the central laboratory) will be summarised by treatment group using the lowest values (for parameters with a lower normal range defined) and the highest values (for parameters with an upper normal range defined) obtained during the ST and ST+LT periods. In order to identify the lowest or highest post-baseline values in a subject all assessments will be considered, even if they do not correspond to a visit-based summary. For the shift tables, the last observation, regardless of post-randomisation rescue, prior to Week 26 or Week 52 will be used if no Week 26 or Week 52 measurement is available, respectively.

Additional shift table summaries for each period compared to baseline will be provided for the following:

- Subjects with electrolytes (Sodium, Potassium, Calcium, Phosphate, and Magnesium) categories of low, normal, and high (based on normal range of central laboratory) will be summarised by treatment group using the highest and lowest values obtained during the period.
- Subjects with Urine Albumin Excretion Categories (UACR) assessments, will be presented for the values at Week 26 (for ST period) or Week 52 (for ST+LT period) versus baseline, based on the following urine albumin to creatinine ratios: 0 - < 30 mg/g (3.4 g/mol) [normoalbuminuria], ≥ 30 mg/g (3.4 g/mol) - < 300 mg/g (33.9 g/mol) [microalbuminuria], ≥ 300 mg/g (33.9 g/mol) [macroalbuminuria]. If the value at Week 26 or Week 52 is not available, the LOCF observation will be used instead.

4.7.3.2 Elevated liver function tests

The following three criteria will be summarised by treatment group for the ST, ST+LT and randomised withdrawal periods in examination of elevated aminotransferases (AT) (ALT and/or AST) and TB:

- (AST or ALT > 3X upper limit of normal [ULN]) and (bilirubin > 1.5X ULN within 14 days on or after AT elevation)
- (AST or ALT > 3X ULN) and (bilirubin > 2X ULN within 14 days on or after AT elevation)
- (AST or ALT > 3X ULN) and {(bilirubin > 2X ULN and no ALP ≥ 2X ULN) within 14 days on or after AT elevation}.

This analysis will be conducted regardless of rescue medication initiation. The summaries will include all data collected up to the cut-offs defined in [Table 8](#). No comparison vs. baseline will be done.

A listing of all AST, ALT and TB results will be provided for subjects with AST or ALT $\geq 3 \times$ ULN and TB $\geq 1.5 \times$ ULN at any point during the study. For these summaries, liver test data obtained after the start of study medication dosing up to and including 30 days after the last blind dosing date (or up to and not including the start of the LT period, whichever comes first, for ST period) will be considered as obtained respectively during ST and the LT the period.

4.7.3.3 Elevated liver tests and/or reported hepatic adverse events

A summary of subjects with elevated liver tests (as defined in Appendix Section [8.7.1](#)) and/or hepatic AEs will be provided by treatment group for the ST, ST+LT and randomised withdrawal periods. The summary will include subjects with AST and/or ALT elevation, TB elevation, combined AT and TB elevation, and ALP elevation. Hepatic AEs (defined prior to database lock) will be summarised by PT, in decreasing frequency of PT according to the overall active arm. A listing of all Hepatic AEs will be presented for the ST+LT period.

4.7.3.4 Marked laboratory abnormalities

Laboratory abnormalities will be evaluated based on MA values for selected parameters (see pre-defined criteria detailed in Appendix Section [8.7.1](#) to identify MAs). If both the baseline and on-treatment values of a parameter are beyond the same MA limit for the parameter, then the on-treatment value will be considered a MA only if it is more extreme (farther from the limit, e.g. worsens) than was the baseline value. If the baseline value is beyond the low MA limit, and the post-baseline value is beyond the high MA limit (or vice-versa), then the post-baseline value will be considered a MA. If baseline value is missing and the post-baseline value is beyond the MA limit, then the post-baseline value will be considered a MA.

Laboratory MAs occurring during the ST, ST+LT, and ST+LT up to Week 32 periods based on Treated Subjects Data Set will be summarised by treatment group. In addition, laboratory MAs will be summarised for the Randomised Withdrawal period based on the Randomised Withdrawal Subjects Data Set, separately for the three treatment comparisons described in Section [4.1.5](#). The summaries will be presented for both the primary and sensitivity safety analyses. The primary analyses of MAs will include data regardless of rescue medication initiation. Additional sensitivity analyses will be provided for MAs occurring prior to rescue medication initiation.

For the ST+LT analysis, incidence rates of marked abnormalities will also be presented.

In addition, laboratory MAs will be summarised using incidence rates by treatment group received at the time of MA onset for the ST+LT period. For placebo subjects re-randomised to switch to dapagliflozin (or saxagliptin), MAs will be analysed in the placebo group to the beginning of the randomised withdrawal period and in the dapagliflozin (or saxagliptin) group if the event onset occurs during the randomised withdrawal period.

The direction of change (high or low) in MA will be indicated in the tables.

In addition, a weighted analysis for the laboratory MAs will also be provided based on the ST+LT period, as described in Section 4.7, to account for the randomised withdrawal design.

Additionally, for each subject with a post-baseline MA for a parameter, all the subject's values of that parameter over the treatment period and the follow-up period, where applicable, will be listed.

4.7.3.5 Fasting lipid panel

Summaries of cholesterol, triglycerides, high density lipoproteins (HDL) cholesterol, and calculated low density lipoproteins (LDL) cholesterol will be provided by treatment group for baseline, Week 26, and Week 52 (ST+LT period analysis) with corresponding changes from baseline, regardless of rescue medication initiation. Lipid panel assessments will also be listed for the ST+LT period. For the ST+LT + Week 104 period, the listing will include all data collected up to Week 104.

4.7.3.6 Pregnancy test results

By-subject listings of pregnancy test results will be provided for the ST+LT period using HCG and serum pregnancy test results from the central laboratory. For the ST+LT + Week 104 period, the listing will include all data collected up to Week 104.

4.7.4 Vital signs

Vital sign measurements for diastolic blood pressure, systolic blood pressure and heart rate at baseline, Week 6, Week 12, Week 14, Week 20, Week 26, Week 32, Week 40, Week 52 and changes from baseline at each visit will be summarised by treatment group using descriptive statistics (including data regardless of rescue medication initiation) for the ST+LT period. In addition, this analysis will also be performed for the randomised withdrawal period using the Randomised Withdrawal Subjects Data Set for the first two treatment comparisons described in Section 4.1.5. Summaries of vital signs data will include assessments up to the cut-off dates defined for each period in Table 8. Visit windows are provided in Section 4.1.7.1 in order to link each vital sign measurement to a scheduled visit.

A listing of vital signs will be provided for the ST+LT period. For the ST+LT + Week 104 period, the listing will include all data collected up to Week 104.

4.7.5 Electrocardiograms

The normality/abnormality (further classified by clinical significance) of the overall ECG interpretation, as determined by the investigator, will be summarised by treatment group based on observed data regardless of rescue medication initiation using frequency tables on number of subjects who have a normal/abnormal ECG tracing at each scheduled time of assessment for the analysis period, overall and by the ECG tracing at baseline. These analyses will be performed for ST+LT treatment period using the LOCF approach.

In addition, a weighted analysis for the normality/abnormality of the overall ECG interpretation will also be provided based on the ST+LT period, as described in Section 4.7, to account for the randomised withdrawal design.

All ECG data will be listed for the ST+LT period.

4.7.6 Body weight, height and BMI

Body weight (kg), height (cm) and BMI (kg/m²) measurements at baseline, Week 6, Week 12, Week 20, Week 26, Week 32, Week 40, Week 52, Week 104 and changes from baseline at each visit will be summarised using descriptive statistics, regardless of rescue medication initiation. Summaries will include assessments performed up to the cut-off dates defined for each period in Table 8. Visit windows are provided in Section 4.1.7.1 in order to link each measurement to a scheduled visit. In addition, normalised height, body weight and BMI expressed as a z-score adjusted for age at the assessment and sex using CDC (see details in Section 3.4.8) will be also be summarised using the same approach.

In addition, body weight, height, and BMI will also be summarised during the randomised withdrawal period using the Randomised Withdrawal Subjects Data Set for the first two treatment comparisons described in Section 4.1.5, and for post-study visit at Week 104 using the Treated Subjects Data Set.

A listing of body weight, height and BMI along with z-scores by subject will be provided. For the ST+LT period this listing will include all data collected up to the end of the LT period. For the ST+LT + Week 104 period, the listing will include all data collected up to Week 104.

4.7.7 Measures of growth and maturity

4.7.7.1 Tanner stages

Tanner stages will be summarised based on observed data, regardless of rescue medication initiation. Summaries of descriptive statistics will be provided for baseline, Week 26, Week 52, and for the post-study visit at Week 104 using the LOCF approach in the period. Changes from baseline at these time points will be provided using shift tables and by visit according to baseline status. Also, change from Week 26 status to Week 52 and change from Week 52 status to Week 104 according to baseline status will be presented. A weighted analysis, as described in Section 4.7, to account for the randomised withdrawal design may also be presented.

In addition, Tanner staging will also be summarised as above during the randomised withdrawal period, using the Randomised Withdrawal Subjects Data Set for the first two treatment comparisons described in Section 4.1.5. Summaries of descriptive statistics will be provided for withdrawal baseline, Week 52 and Week 104 using the LOCF approach. Changes from withdrawal baseline at Week 52 and Week 104 will be provided using shift tables, for Week 52 and Week 104 according to withdrawal baseline status and also for Week 104 according to Week 52 status.

4.7.7.2 Puberty status

Puberty status (as defined in Appendix Section 8.10.3) will be summarised regardless of rescue medication initiation at Week 26 and Week 52, where the height velocity is based on change from baseline, and Week 104, where the height velocity is based on change from Week 52.

4.7.7.3 Growth and maturity markers

Summaries of growth and maturation markers (see Section 3.4.9) in SI and conventional units will be based on observed data, regardless of rescue medication initiation. Descriptive summaries of absolute values and changes from baseline (where applicable) will be provided for baseline, Week 26, Week 52, and for the post-study visit at Week 104 using the LOCF approach. For the Week 104 analyses, change from Week 52 will also be presented.

In addition, growth and maturation markers will also be summarised during the randomised withdrawal period using the Randomised Withdrawal Subjects Data Set for the first two treatment comparisons described in Section 4.1.5. Descriptive summaries of absolute values and changes from withdrawal baseline (where applicable) will be provided for withdrawal baseline, Week 52 and Week 104 using the LOCF approach.

A categorical change from baseline summary will also be produced by treatment group, age category (≥ 10 and < 15 years, ≥ 15 and < 18 years) using the randomisation strata, and puberty status at Week 26, Week 52 and Week 104 (as defined in Appendix Section 8.10.3) for Week 26, Week 52, and for the post-study visit at Week 104 using the LOCF approach. Similarly, a categorical change from withdrawal baseline summary will also be produced for the Randomised Withdrawal Subjects Data Set for Week 52 and Week 104 using the LOCF approach.

A listing of the growth and maturation markers along with the Tanner stages by subject will be provided. For the ST+LT period this listing will include all data collected up to the end of the LT period. For the ST+LT + Week 104 period, the listing will include all data collected up to Week 104.

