1.3.3 Safety Objectives

- To assess the safety and tolerability, including the incidence of adverse events (AEs) and
 events of hypoglycemia, of dapagliflozin and saxagliptin as add-on to diet and exercise and
 metformin (IR or XR), or insulin, or metformin (IR or XR) plus insulin in pediatric T2DM
 subjects when administered for up to 26 weeks of short-term (ST) double-blind treatment, and,
 separately, up to 52 weeks of total treatment.
- To assess the incidence of diabetic ketoacidosis (DKA) with dapagliflozin and saxagliptin as
 add-on to diet and exercise and metformin (IR or XR), or insulin, or metformin (IR or XR)
 plus insulin in pediatric T2DM subjects when administered for up to 26 weeks of ST doubleblind treatment, and, separately, up to 52 weeks of total treatment.
- To assess measures of growth and maturity and Tanner staging and markers of bone health in pediatric T2DM subjects when administered dapagliflozin or saxagliptin as add-on to diet and exercise and metformin (IR or XR), or insulin, or metformin (IR or XR) plus insulin for up to 26 weeks of ST double-blind treatment, and, separately, for up to 52 weeks of total treatment, and for an additional 52 weeks after the study has been completed and study-related treatment has been discontinued.
- To assess the safety and tolerability of dapagliflozin (or saxagliptin) monotherapy in pediatric subjects who are randomized to withdraw background metformin.

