- Eligible subjects who are receiving active treatment will be grouped into two separate strata for saxagliptin and dapagliflozin, and then randomized 1:1 within each strata to either discontinue background medication with metformin or to continue background medication with metformin. For subjects on active treatment who are randomized to withdraw background treatment with metformin, those who are currently receiving high doses of saxagliptin (5 mg) or dapagliflozin (10 mg) will continue to receive the high doses, whereas subjects who are currently receiving low doses of saxagliptin (2.5 mg) or dapagliflozin (5 mg) will have their doses up-titrated to the high doses (saxagliptin 5 mg or dapagliflozin 10 mg). Subjects in the active treatment arms who are randomized to continue background medication with metformin will continue with their current dose of either saxagliptin or dapagliflozin (Figure 3.1-2).
- Eligible subjects who are receiving placebo will be randomized 1:1:1 to either withdraw background medication with metformin and switch to active treatment with either saxagliptin 5 mg or dapagliflozin 10 mg or to remain on background medication with metformin and continue with placebo (Figure 3.1-2).

Discontinuation of background metformin will occur in an unblinded manner. Exposure to monotherapy in subjects undergoing randomized withdrawal of metformin will last from the start of metformin withdrawal for that subject (following randomization at Week 32 or Week 40) until the end of Week 52, when all subjects will discontinue study medications. After Week 52, all subjects will take the most appropriate medication at the discretion of the treating physician.

Rescued subjects and subjects who discontinue IP will not be eligible for randomized withdrawal of background medication at Week 32 or Week 40.

Subjects with $HbA1c \ge 7.5\%$ at Week 26 and Week 32 and subjects who are receiving background treatment with either insulin only, or insulin+metformin, including those randomized to receive placebo, will continue their randomized study medication assigned after the Week-12 assessment in the double-blind LT treatment period.

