3.4.9 Measures of growth and maturity

Measures of growth and maturity include Tanner staging and central laboratory evaluations of growth and maturation markers and bone biomarkers. These will be assessed during the lead-in visit (Tanner staging only) or Day 1 prior to first dose (growth, bone and maturation markers only), and at Week 26, Week 52, Week 104, and (if applicable) at the ETD, Rescue and non-treatment follow-up visits.

Tanner staging is a measure of pubertal development rated on a scale of stage 1 to stage 5 (for details see Appendix Section 8.10.1). Tanner staging will be determined based on investigator assessment and the subjects' self-reports.

Growth and maturation markers

- Thyroid-stimulating hormone (TSH),
- Free thyroxine (assessed at Screening if TSH is abnormal),
- Luteinising hormone (LH) (females only),
- Follicle-stimulating hormone (FSH) (females only),
- Oestradiol (females only),
- Total testosterone (males only),
- Insulin-like growth factor-1 (IGF-1),
- Insulin-like growth factor binding protein-3 (IGFBP-3),
- Calcitonin,
- 25-hydroxy vitamin D.

Bone biomarkers

- Bone alkaline phosphatase,
- Osteocalcin,
- Parathyroid hormone (PTH),

- Carboxyterminal cross-linked telopeptide of Type 1 collagen (CTX-1).

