4.1.1 Definitions

Baseline

Unless stated otherwise, for each subject, baseline value of a parameter (e.g., efficacy laboratory parameter, safety laboratory test, ECG or physical measurement endpoint) is defined as the last assessment on or prior to the date of the first dose of the double-blind study medication in the ST treatment period (Day 1).

If there are multiple assessments with the same date and time, the average value will be used as baseline.

For subjects belonging to the Randomised Withdrawal Subjects Data Set, the withdrawal baseline value for a given parameter is defined as the closest available value on or before the day of first dose in the Randomised Withdrawal period.

Change from baseline

Change from baseline to any Week t in the analysis period (i.e., ST treatment period and ST+LT treatment period) is defined as follows:

$C_{Week\ t} = M_{Week\ t} - M_{baseline}$,
where:

- $C_{Week\ t}$ is the change from baseline at Week t ,
- $M_{Week\ t}$ is the measurement at Week t ,
- $M_{baseline}$ is the measurement at baseline.

The “Week t ” to which a measurement belongs is determined using the conventions described in [Table 8](#) (Section 4.1.6).

Last observation carried forward (LOCF)

A post-baseline missing value will be imputed by the last available non-missing post-baseline or post-withdrawal baseline (as applicable) value. If the first scheduled post-baseline or post-withdrawal baseline value is missing, no imputation will be done.

Day 1 is the date of first dose of study drug in the ST period.

Study day is defined relative to the date of first dose (Day 1) received in ST treatment period, and is calculated as:

- If assessment date is before the date of first dose: assessment date - date of first dose in the ST period (Day 1).
- If assessment date is on or after the date of first dose: assessment date - date of first dose in the ST period (Day 1) + 1.

Treatment response to HbA1c

A treatment responder at Week t is a subject with HbA1c $< 7\%$ at Week t (irrespective of baseline value). HbA1c response at Week t will be derived by dichotomising HbA1c values at Week t (binary variable, set to 1 if HbA1c $< 7\%$ at Week t and 0 if HbA1c $\geq 7\%$ at Week t). Where specified, missing HbA1c responses at Week t will be derived from imputed continuous values of HbA1c for Week t .

Rescue medication initiation

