4.7.7.4 Bone biomarkers

Summaries of bone biomarkers (see Section 3.4.9) in SI and conventional units will be based on observed data, regardless of rescue medication initiation. Descriptive summaries of absolute values and changes from baseline (where applicable) will be provided for baseline, Week 26, Week 52, and for the post-study visit at Week 104 using the LOCF approach. For the Week 104 analyses, change from Week 52 will also be presented.

In addition, bone biomarkers will also be summarised as above for subjects going through the third randomisation using the Randomised Withdrawal Subjects Data Set for the first two treatment comparisons described in Section 4.1.5.

A categorical change from baseline summary will also be produced by treatment group, age category (≥ 10 and < 15 years, ≥ 15 and < 18 years) using the randomisation strata, and puberty status at Week 26, Week 52, and Week 104 (as defined in Appendix Section 8.10.3) for Week

26, Week 52, and for the post-study visit at Week 104 using the LOCF approach. Similarly, a categorical change from withdrawal baseline summary will also be produced for the Randomised Withdrawal Subjects Data Set for Week 52 and Week 104 using the LOCF approach.

A listing of the bone biomarkers along with the Tanner stages by subject will be provided. For the ST+LT period this listing will include all data collected up to the end of the LT period. For the ST+LT + Week 104 period, the listing will include all data collected up to Week 104.

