Parameter	Assessment	Short term period	Short term + Long term period	Withdrawal period: 1) For subjects initially randomised the dapagliflozin (or saxagliptin) group: High-dose dapagliflozin (or saxagliptin) vs High-dose dapagliflozin (or saxagliptin) + Metformin 2) For subjects initially randomised to the placebo group: High-dose dapagliflozin (or saxagliptin) vs Placebo + Metformin 3) Based on third randomisation (regardless of prior treatments)	Post-study visit Week 104
	Growth and maturity markers		Descriptive statistics Based on LOCF values Regardless of rescue Treated Subjects Data Set	Descriptive statistics Regardless of rescue Based on LOCF values Randomised Withdrawal Subjects Data Set Treatment regimens 1 and 2	Short term + Long term + Week 104: Descriptive statistics Regardless of rescue Based on LOCF values Treated Subjects Data Set
				Categorical change from withdrawal baseline by age and puberty status Regardless of rescue Randomised Withdrawal Subjects Data Set Treatment regimens 1 and 2	Short term + Long term + Week 104: Categorical change from baseline by age and puberty status Regardless of rescue Treated Subjects Data Set

Parameter	Assessment	Short term period	Short term + Long term period	Withdrawal period: 1) For subjects initially randomised the dapagliflozin (or saxagliptin) group: High-dose dapagliflozin (or saxagliptin) vs High-dose dapagliflozin (or saxagliptin) + Metformin 2) For subjects initially randomised to the placebo group: High-dose dapagliflozin (or saxagliptin) vs Placebo + Metformin 3) Based on third randomisation (regardless of prior treatments)	Post-study visit Week 104
	Bone biomarkers		Descriptive statistics Based on LOCF values Regardless of rescue Treated Subjects Data Set	Descriptive statistics Regardless of rescue Based on LOCF values Randomised Withdrawal Subjects Data Set Treatment regimens 1 and 2	Short term + Long term + Week 104: Descriptive statistics Regardless of rescue Based on LOCF values Treated Subjects Data Set
				Categorical change from withdrawal baseline by age and puberty status Regardless of rescue Randomised Withdrawal Subjects Data Set Treatment regimens 1 and 2	Short term + Long term + Week 104: Categorical change from baseline by age and puberty status Regardless of rescue Treated Subjects Data Set

Statistical Analysis Plan
Study Code CV181375/D1680C00019
Edition Number 5.0
Date 07 DEC 2022

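### LOCF fills missing Week 104 growth, maturation and bone markers, so for a child treated to Week 52 an end-of-treatment value can stand as the post-treatment reading

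*SAP*

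**What the plan says.** The protocol's safety objectives (1.3.3) ask for growth, maturity and bone markers on treatment and "for an additional 52 weeks after the study has been completed and study-related treatment has been discontinued". Protocol 3.1 fixes the end of Week 52 as the point "when all subjects will discontinue study medications".

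SAP 3.4.9 schedules marker samples on Day 1 "and at Week 26, Week 52, Week 104, and (if applicable) at the ETD, Rescue and non-treatment follow-up visits".

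SAP 4.7.7.3 tabulates growth and maturation marker values, with their changes from baseline, at the scheduled visits. The last of these is given as "for the post-study visit at Week 104 using the LOCF approach. For the Week 104 analyses, change from Week 52 will also be presented". SAP 4.7.7.4 uses the same wording for bone markers, after saying that their summaries "will be based on observed data, regardless of rescue medication initiation". Both sections also apply LOCF at Week 104 to the categorical changes from baseline and from withdrawal baseline.

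SAP 4.1.1 defines the method: "A post-baseline missing value will be imputed by the last available non-missing post-baseline or post-withdrawal baseline (as applicable) value". It adds one exception: "If the first scheduled post-baseline or post-withdrawal baseline value is missing, no imputation will be done". Neither sentence stops the carry at the end of a study period. Table 24 (SAP 8.15) lists the Week 104 marker summary as "Short term + Long term + Week 104: Descriptive statistics Regardless of rescue Based on LOCF values Treated Subjects Data Set".

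**The concern.** The Week 104 column exists to show what happens after drug is stopped. The LOCF rule has no period limit and Table 24 pools the short-term, long-term and Week 104 data, so a Week 52 sample can be carried across the end of treatment into that column. Table 10 opens the Week 104 window only after Week 56, so LOCF is the only route by which a Week 52 value can get there.

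For a child treated to Week 52, that puts an end-of-treatment measurement where a post-treatment one is wanted. It pulls any recovery or rebound toward no change, and in growing adolescents no change is not a neutral assumption. Unequal loss to follow-up could also make arms look different when they are not.

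The SAP is not consistent on this. The marker paragraphs claim observed data and then impute. Height, weight and BMI (SAP 4.7.6) have no LOCF. For height velocity, SAP 8.10.2 extrapolates a missing Week 104 height from the two preceding observations. The categorical marker tables are split by Week 104 puberty status, which for Tanner stage 4 depends on height velocity, so a marker held flat may be tabulated against an extrapolated height.

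**Working it through.** The plan gives no figure on this point to reproduce. The check applies the SAP 4.1.1 rule to the scheduled visits and then works out the effect on the column mean.

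**Step 1. Single children.** Illustrative values at Day 1, Week 26, Week 52 and Week 104:

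- (10, 12, 15, 19): nothing is imputed and the change from Week 52 is 19 - 15 = 4.
- (10, 12, 15, missing): Week 104 becomes 15. Change from Week 52, if taken on LOCF values, is 15 - 15 = 0.
- (10, 12, missing, missing): Week 52 and Week 104 both become 12. The change is 0 if the Week 52 reference may itself be LOCF. If an observed Week 52 value is required, the child drops out of that summary.
- (10, missing, 15, missing): the change is 0, unless the exception for a missing first post-baseline value is read as blocking all imputation.
- (10, missing, missing, missing): nothing is imputed and the child does not contribute.

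**Step 2. Change from Week 52.** Let d be the mean change in children with both samples and f the share of the column carried forward. Each carried child contributes 0, so

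column mean = (1 - f) x d + f x 0 = (1 - f) x d.

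The documents do not give f, so the values below are assumptions. The last column takes the planned 81 per arm as the denominator.

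| f | Column mean | Children entered as 0 |
|---|---|---|
| 5% | 0.95d | 81 x 0.05 = about 4 |
| 10% | 0.90d | 81 x 0.10 = about 8 |
| 20% | 0.80d | 81 x 0.20 = about 16 |
| 30% | 0.70d | 81 x 0.30 = about 24 |
| 40% | 0.60d | 81 x 0.40 = about 32 |

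At f = 0 there is no effect.

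**Step 3. Spread.** If d = 0, the SD of the change is multiplied by the square root of (1 - f): 0.975 at 5% and 0.775 at 40%. If d equals one SD, the multipliers are 0.999 and 0.917. The understatement of spread is therefore modest unless f is large.

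**Step 4. Two arms.** With the same d in both arms and assumed f of 10% and 30%, LOCF alone produces 0.90d - 0.70d = 0.20d.

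**Step 5. Change from baseline at Week 104.** LOCF is explicit here. If b is the mean change from baseline to Week 52 and all children share the same b and d, the column shows (1 - f)(b + d) + f x b = b + (1 - f)d. It falls short of b + d by f x d.

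**The case against.** The strongest reply is that the plan already contains a remedy. SAP 4.1.5 repeats the Week 104 analyses in children who had the Week 104 visit, and marker listings up to Week 104 are planned. This stands as real mitigation, because in that repeat every child who missed the visit is gone. It is not complete. The full-set table remains, and completers are defined by the visit, so an attender without a marker sample is still filled.

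Second, the sentence on change from Week 52 does not itself mention LOCF, and its paragraph opens by claiming observed data. This also stands: the zero change is a reading of the text, not a stated rule. The Week 104 values and changes from baseline are LOCF in so many words.

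Third, the tables are descriptive, have no hypothesis test, and come from a separate Week 104 database lock (SAP 1.6). Table 10 accepts any sample taken after Week 56, which should keep f down. Observed-only summaries are also selective if loss depends on outcome. All of this stands, but an observed summary with its n shows the gap and does not fill it.

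A reader might infer three stronger points, which the documents do not support:

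- **That every carried value is an on-drug value.** Markers are also taken at early-discontinuation and non-treatment follow-up visits, and SAP 4.1.7 applies no cut-off dates to Week 104 presentations. For an early stopper, the carried value may already be off treatment. For a child who stayed on placebo, it is a placebo-period value.
- **That every child without a Week 104 sample counts as zero.** The exception in SAP 4.1.1 leaves some children unimputed.
- **That LOCF spoils the Week 52 column in the same way.** There, the Table 8 cut-off of 4 days after the Week 52 or early-discontinuation date removes later samples, and Table 10 assigns marker samples from the start of the long-term period to Week 52. Deleting LOCF would not restore what the cut-off drops.

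**Conclusion.** The concern holds for Week 104. As written, the full-set tables can enter an end-of-treatment marker value as the post-treatment reading for a child treated to Week 52, against the SAP's own statement that they use observed data. If change from Week 52 is taken on LOCF values, its mean shrinks to (1 - f) of the change in children actually sampled: 0.95 to 0.60 for f of 5% to 40%. That range is assumed, because the documents give neither f nor the size of the change. The between-arm figure of 0.20d is likewise only an illustration. The consequence is attenuation in a descriptive safety summary. No error rate or efficacy conclusion is affected. It should still be corrected, because the bias runs toward no change in the one column meant to show change after stopping drug.

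**What to change.** In SAP 4.7.7.3, 4.7.7.4 and Table 24, remove LOCF for growth, maturation and bone markers at Week 104. Do this in both the baseline and the withdrawal-baseline tables, including the categorical changes. Summarise observed Week 104 samples with n, and compute change from Week 52 only in children with observed samples at both visits.

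For Tanner stage (SAP 4.7.7.1), state that the within-period qualifier on LOCF means nothing is carried past Week 56. Apply the same limit to the unqualified LOCF sentence for the Randomised Withdrawal Subjects Data Set.

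The cost is SAP wording and table programming, and a smaller n at Week 104. No new data are needed.
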